5. STUDY DESIGN

Stepped-wedge open-label, non-randomized, cluster intervention.

This study will be performed in clusters (hamlet (isolated group of household, village, or group of village). The intervention will be conducted in two types of clusters, both corresponding to locations where an excess of case was detected.

Group 1: Sustained high incidence clusters, characterized by a yearly cumulative incidence >84 cases/1000/year

Villages in group 1 will be attributed an intervention a given year based on the cumulative incidence over the previous 12 months (METF stratification January, including the last 2 transmission seasons). The order of intervention will be decided based on logistic constraints and highest incidence.

Group 2: Focal transmission clusters, corresponding to locations where an epidemic alert has been signalled and confirmed (see definition of thresholds).

*Villages in group 2 will be attributed an intervention based on *P. falciparum* incidence in the previous 4 weeks. In near-0 transmission area, an intervention will be conducted in each likely source location of transmission of a locally acquired case. In the other areas (METF1+METF2), the intervention will be triggered when the incidence is above the pre-defined epidemic threshold.*

In each cluster, all inhabitants will be invited to undergo an URDT test to identify their infection status, and will receive the appropriate treatment according to their characteristics. Information on village inhabitants absent during the MSAT activities will be obtained from village population lists provided by the village headman and from household member declarations. During the URDT screening, all individuals will receive a unique identifying number that will be used to record demographic data in the MSAT paper logbook and to label URDT and reference sample.

Before and after MSAT intervention, incidence of clinical malaria episodes will be recorded at the MP (1 or several) serving the cluster receiving the intervention. No individual data will be collected to link clinical case participation, infection status and incidence of clinical episodes.

Participants from group 1 clusters will also be invited to participate in a prevalence survey during MSAT and 12 months after, in order to evaluate the impact of the MSAT campaign on the asymptomatic carriage prevalence. This will require collection of a 50µL sample during the MSAT campaign and a second round of URDT screening with the collection of a 50µL sample, 12 months after MSAT.

6. PARTICIPANT IDENTIFICATION AND RECRUITMENT

6.1. Study villages selection

The study village selection is based on the definition of three main strata of *P. falciparum* incidence corresponding to different probabilities of rapid elimination. Based on 2017 data, the townships of Myawaddy, Hlaingbwe and Kawkareik have almost interrupted *P. falciparum* transmission (95% of villages with 0 incidence), while heterogeneity persists in Hpapun township with diverse transmission and incidence profiles.

6.1.1. Group 1: sustained high incidence villages

Villages classified as high incidence, low probability of elimination (*P. falciparum* cumulative incidence >84 cases/1000/year, in spite of >1 year of functioning malaria post) will be eligible to be included in group 1. Villages in this group will be addressed by MSAT waves of 10-15 villages.

Villages will be included in a given wave based on accessibility to the team and proximity from each other, as well as requirements for the program impact. Wave 1 will include 5 villages and be conducted during first semester 2018, after which a maximum of two waves will be conducted per semester.

6.1.2. Group 2: seasonal focal transmission villages/locations

This group will follow the NMCP case/and foci investigation guidelines, but use URDT instead of standard RDT for screening. MSAT group 2 locations will be cluster of houses, villages or clusters of villages selected based on the results of case or foci/outbreak investigation.

6.1.2.1 Village inclusion after case investigation

Case investigation will be performed systematically in the three townships of Myawaddy, Kawkareik and Hlaingbwe, upon notification of ≥ 1 *P. falciparum* clinical case. The aim will be to determine the most likely location of transmission.

The village or cluster of houses corresponding to the most likely location of transmission will be included in group 2 if it is located in Myawaddy, Kawkareik and Hlaingbwe.

The most likely location of transmission will not be included in group 2 if it is located outside METF area, or in Hpapun township.

However, upon evolution of the overall incidence, subdivisions of Hpapun township reaching 0-transmission will be included in the case investigation activities and therefore eligible for case investigation and inclusion in group 2 MSAT.

6.1.2.2 Village inclusion after outbreak investigation

Outbreak alarms will be generated from Hpapun township by the analysis of weekly *P. falciparum* incidence data by METF surveillance system (e.g. following thresholds such as cases >90th percentile at the village or cluster level). An investigation will be conducted to determine the context of transmission and assess the contribution of imported case in this increase.

The cluster will be included in group 2 if the investigation concludes to the existence of a local increased transmission episode.

6.2. Study Participants

Since the study will be performed at cluster/village level, the population of study villages will be included and monitored as a whole for the primary outcome on falciparum malaria incidence in the village. Likewise, change in prevalence will be measured by a follow-up survey at village level without matching individuals from MSAT screening to follow-up survey.

MSAT intervention and follow-up surveys will be conducted on individual participants. All population of the cluster/village will be eligible for participation in the MSAT campaign. For the follow-up survey, only residents living in the village for >1 months will be considered in order to assess the reservoir in the village population and limit the contribution of imported carriage.

6.3. MSAT intervention

6.3.1. Inclusion criteria

All persons living in the village or cluster of villages will be eligible for MSAT intervention. Individuals living in smaller settlements (permanent or temporary) within walking distance of a selected intervention village will also be eligible.

Large “work-related” settlements in the vicinity of a targeted village (military camps, logging camp, mining site) will be approached by the team to be included in the screening and treatment activity. They will be included in the analysis as a unit within a cluster of villages if all the study information can be collected (including follow-up survey for Group 1).

6.3.2. Exclusion criteria

- Individuals who do not provide informed consent for both URDT screening and treatment in case of positive result. Individuals will be given the possibility to refuse the collection of the 50µL reference sample or the DBS collection but participate to URDT screening and treatment.
- Children <1 year old
- Individuals with a documented Pf-positive malaria RDT who received treatment (AL+slid PMQ) during the previous 7 days.

NB: Individuals who were diagnosed infected with PF and received a treatment between 7 and 30 days before the intervention are still likely to be URDT positive due to the persistence of HRP2, and this will result in treatment of individuals who are likely uninfected. However, in a high prevalence area or in an outbreak context, previous infection signals exposure, and DP will provide a protection against a likely re-infection.

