4. OBJECTIVES AND OUTCOME MEASURES

Objectives	Outcome Measures	Timepoint(s) of evaluation of this outcome measure (if applicable)
Primary Objective To measure the impact of URDT-based MSAT on P. falciparum incidence at village-level.	Adjusted incidence rate ratio before/after MSAT	Follow-up from MP opening to end of study
Secondary Objectives 1) To measure the impact of MSAT on prevalence of P. falciparum infection in malaria hotspots	1) Prevalence of P. falciparum infection measured in the village by URDT and by reference method (group 1)	1) Comparison between M0 survey (during MSAT) and M12 survey (12 months after)
2) To measure the impact of reactive MSAT on incidence of seasonal malaria peaks / outbreaks.	2) Change in the incidence dynamics over the transmission season (group 2)	2) Duration and height of seasonal peak before, during and after reactive intervention
3) Feasibility of MSAT as a programmatic tool and as a reactive strategy.	3) Coverage of village population with intervention	3) coverage based on census conducted before/during MSAT
4) % of infections treated compared to infections detected by reference method	4) % of P. falciparum positive samples by reference method which were positive by URDT and treated; % of P. falciparum negative samples by reference method which were positive by URDT and treated (group 1)	Group 1 only
Tertiary Objectives Retrospective comparison of MSAT versus MDA on prevalence and incidence of P. falciparum malaria	Cumulative incidence of falciparum malaria episodes before and after MDA/MSAT; prevalence of falciparum infection before and after MDA/MSAT	Entire incidence series

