6.4.2. Exclusion criteria

- Individuals who do not provide informed consent.
- Individuals who have lived in the village for less than 4 weeks (newcomers residing elsewhere before)

- Individuals who had a falciparum positive RDT and received a complete ACT-treatment course during the 3 weeks before the survey.

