7.5. Baseline Assessments

The baseline assessment (D0) will occur immediately after inclusion. Participants will be asked baseline demographic data (age, sex, visitor status, occupation and activities during the previous month) and baseline clinical data (temperature and history of fever over the previous week), which will be recorded in a logbook where each patient will be identified by a unique number printed on a sticker that will also be used to label the URDT, the sample(s) collected from the participant.

In **group 1 only**, participants will undergo a finger-prick from which capillary blood will be collected using the lancet provided by the URDT manufacturer in order to realize the URDT. From the same finger-prick, 50 μ L of capillary blood will also be collected on an EDTA microtube, labelled with a participant sticker.

The URDT will be read by a trained field worker following the manufacturer's instructions. If the test is positive, a second finger prick will be conducted in order to collect an additional blood sample on filter paper (3x 1cm blood spots), labelled with a participant sticker.

If the test is positive, a physical and clinical examination will be conducted. Female participants of child-bearing age will be asked if they are or could be pregnant and proposed to take a pregnancy test if unsure. History of malaria diagnosis and treatment during the previous week will be collected. The weight of the participant will be measured and history of previous allergies to drugs and specifically antimalarials will be collected. A curative treatment for *P. falciparum* malaria will be administered to falciparum-positive participant following a weight-adjusted dosage and according to each participant characteristics (see 8. intervention).

The willingness and ability of eligible participants to take a complete treatment will be assessed by the fieldworker, and the importance of completing the treatment will be discussed with the participant if

necessary. The first dose of treatment will be administered directly, and recorded in the logbook. An appointment will be set for the next dose on the following day.

Participants who declare being unable to attend supervised treatment for the next takes will be given the remaining doses (expected <2.5% of treatments initiated).

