9.3. Analysis of Outcome Measures

Primary outcome: stepped-wedge comparison of incidence.

The incidence comparison will be conducted over a 2-year series of weekly incidence data, corresponding to 12 months before and 12 months after MSAT intervention. A generalized additive multilevel mixed model will be used to adjust for location, season, and temporal trend due to MP activity using uni-(seasonality, duration of MP activity in the village) or bivariate (latitude and longitude) splines, including random intercept and slopes at village level. MSAT intervention will be included in the model as a 0-1 variable. The incidence rate ratio obtain for this variable will quantify the average decrease in incidence after MSAT campaign compared to before.

Secondary outcome: before-after comparison of prevalence

For each village, the fractional change in prevalence before MSAT and 12 months after will be calculated and compared to 0% change. This change will be compared to the fractional change observed after MDA.

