17. APPENDIX B: SCHEDULE OF STUDY PROCEDURES

Procedures	Visits (insert visit numbers as appropriate)					
	Day 0					
Informed consent	Day 0					
Demographics	Day 0					
Malaria history over previous 3 weeks	Day 0					
Temperature	Day 0					
Falciparum URDT (+50µL sample collection in group 1)	Day 0					
Falciparum positive participant						
Clinical examination	Day 0					
Treatment	Day 0	Day 1	Day 2	*		
Passive AE follow-up (study team/MPW)	Day 0	Day 1	Day 2	Day 3	Day 4	
All participants						
Passive incidence data collection	Day 0				Daily	Day 365
Group 1 villages						
Demographic data collection	Day 0					Day 365
M12 follow-up survey in group 1: URDT+50µL sample collection						Day 365
*a longer follow-up may be required for patients receiving specific regimen other than standard MDA treatment (DP3+sldPMQ) or standard first-line treatment for clinical cases (AL3+sldPMQ).						

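### Group 1's M0 and M12 prevalence surveys exclude recently treated people over different windows (7 days and 3 weeks), which probably makes the fall in prevalence look slightly too large

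*Combined protocol and SAP*

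**What the plan says.** The M0 prevalence survey in group 1 is the MSAT screening itself. Section 4 gives the evaluation as "Comparison between M0 survey (during MSAT) and M12 survey (12 months after"), and section 5 says group 1 participants "will also be invited to participate in a prevalence survey during MSAT and 12 months after". M0 therefore takes on the MSAT exclusions.

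- **M0 (6.3.2):** excluded are "Individuals with a documented Pf-positive malaria RDT who received treatment (AL+slid PMQ) during the previous 7 days". The NB below adds that people treated 7 to 30 days before "are still likely to be URDT positive due to the persistence of HRP2" and are probably uninfected. It accepts treating them because DP protects against re-infection.
- **M12 (6.4.2):** excluded are "Individuals who had a falciparum positive RDT and received a complete ACT-treatment course during the 3 weeks before the survey".
- **Tests:** section 4 names URDT and the reference method. Section 7.7 gives the reference as Quansys ELISA, and Appendix D, Table 2 labels that result as HRP2.
- **Analysis (9.3):** for each village, "the fractional change in prevalence before MSAT and 12 months after will be calculated and compared to 0% change". No restriction or adjustment for recent treatment is stated.
- **History at M0:** section 7.5, in the paragraph on positive tests, states "History of malaria diagnosis and treatment during the previous week will be collected". Appendix B lists "Malaria history over previous 3 weeks" at Day 0, above the rows reserved for positive participants.

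**The concern.** Someone treated 7 to 21 days before the survey is in both numerator and denominator at M0 but in neither at M12. If residual HRP2 keeps that person positive, M0 prevalence is raised with no matching rise at M12. Both tests named in section 4 detect HRP2, so the reference assay does not remove the artefact. The NB in 6.3.2 justifies treating these people; it does not consider the prevalence comparison.

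The shift is systematic, so more villages do not reduce it, and 9.3 tests the change against 0%. Group 1 is selected for high clinical incidence, so recently treated people are relatively common at M0. Whether M0 can later be put on the M12 definition depends on the history taken. A one-week history in URDT positives cannot identify people treated on days 7 to 21, nor correct the denominator; a 3-week history in everyone could.

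**Working it through.** **The plan's own figure.** Section 9.2.2.2 gives 43 clusters for 16% against 8%, 60 samples per cluster, ICC 0.15, alpha 0.05 and power 0.8.

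- Per period: [1.96·√(2·0.12·0.88) + 0.8416·√(0.16·0.84 + 0.08·0.92)]² / 0.08² = 258.
- Design effect: 1 + 59·0.15 = 9.85.
- Clusters: 258·9.85/60 = 42.4, so 43. The figure reproduces.

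**Inputs for the bias.**

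- Incidence: 250/1000/year (9.2.1), 125/1000/year (pre-MDA average, 9.2.3) and 84/1000/year (group 1 entry threshold).
- Village size 190; 60 villages; reference prevalence 16%.
- Assumptions: cases are spread evenly over the year, and a share *s* of 50-100% of those treated on days 7 to 21 is still positive. The protocol says only that this is likely.

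**People in the gap.** f = incidence × 14/365.

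- 250/1000: f = 0.00959, or 1.8 per village and 109 over 60 villages.
- 125/1000: f = 0.00479.
- 84/1000: f = 0.00322, or 0.6 per village and 37 over 60 villages.

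**Spurious fall with no true change.** M0 on the M12 window is h = (p0 − f·s)/(1 − f); the spurious fall is 1 − h/p0.

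| p0 = 16% (reference) | s = 0.5 | s = 1 |
|---|---|---|
| 250/1000 | h = 15.67%, fall 2.1% | h = 15.19%, fall 5.1% |
| 125/1000 | h = 15.84%, fall 1.0% | h = 15.60%, fall 2.5% |
| 84/1000 | h = 15.89%, fall 0.7% | h = 15.73%, fall 1.7% |

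At 250/1000 a true 50% fall would read as 1 − 0.5·h/0.16 = 51.0% to 52.5%.

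**URDT.** The plan gives no group 1 URDT prevalence, so I back-calculate it from 16% by ELISA with the Appendix D accuracy figures.

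- uPCR prevalence: (0.16 − 0.039)/(0.830 − 0.039) = 15.3%.
- Field URDT: 0.396·0.153 + 0.007·0.847 = 6.7%.
- Lab URDT: 0.558·0.153 + 0.011·0.847 = 9.5%.

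With the same formula:

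- 250/1000: from 4.1% (p0 = 9.5%, s = 0.5) to 13.6% (p0 = 6.7%, s = 1).
- 125/1000: from 2.1% to 6.8%.

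**Offset from the word complete in 6.4.2.** Read literally, someone in mid-course is excluded at M0 but kept at M12. For a 3-day course, g = 0.25·3/365 = 0.00205. If all are positive, M12 becomes (h + g)/(1 + g), which is 15.84% or 15.36%. The spurious fall by reference method at 250/1000 drops from 2.1-5.1% to 1.0-4.0%. Unfinished courses offset more.

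**Effect on the sample size.** Using the harmonised M0 at 250/1000, a 50% fall needs 44 to 45 clusters rather than 43. Group 1 plans 60 villages.

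**The case against.** The strongest reply is that the difference is too small to matter. Against a design built to detect a 50% fall, 1-5% by the reference method would not change the conclusion, and 250/1000/year is a planning assumption at the high end. That stands, and it sets the grade. It does not remove the point, because the shift is systematic, URDT is affected more, and the remedy is cheap.

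A second reply is that the plan can already correct this. Appendix B schedules a 3-week history at Day 0, apparently for everyone; the 6.3.2 exclusion needs recent treatment to be checked before testing; and section 10.2 lists individual falciparum clinical case data among the data entered. This stands in part. Appendix B does not say that treatment is recorded, section 7.5 differs on both window and who is asked, section 5 says no individual data will link infection status to clinical episodes, and 9.3 does not use any of it.

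Several stronger readings are tempting but unsupported:

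- *The bias can only favour MSAT.* The complete-course wording in 6.4.2 works the other way, so the net direction is probable rather than certain.
- *The URDT distortion could reach 18%.* That figure, 1 − [(0.05 − 0.00959)/(1 − 0.00959)]/0.05, needs 5% positivity, 250/1000/year and full persistence together. The 5% is the bottom of a range given for MSAT generally; Appendix D points to about 6.7-9.5% for group 1.
- *A seasonal peak makes it worse.* Section 7.1 revises the group 1 list after each transmission season, so an off-peak M0, with a smaller effect, is at least as possible.
- *The comparison with MDA is biased.* The MDA surveys' exclusions are not given, so the effect there is unknown.

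**Conclusion.** The inconsistency is real and the point is minor. Followed as written, the plan counts at M0 a group that it removes at M12 and that it expects to be falsely positive; the net effect probably exaggerates the fall in prevalence.

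With no true change, the spurious relative fall by the reference method is about 2-5% at 250/1000/year, 1-2.5% at 125 and 0.7-1.7% at 84. At 250/1000/year it is about 1 percentage point less if people in mid-course are counted at M12. By URDT it is about 4-14% at 250/1000/year and 2-7% at 125, before any such offset. These figures rest on the assumed 50-100% persistence, even incidence through the year, and URDT positivity derived from Appendix D.

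A reader might infer that the trial's main result or its ability to show a halving of prevalence is in doubt. The documents do not support that: the primary outcome is clinical incidence recorded at malaria posts, which these survey exclusions do not touch, and a true 50% fall would still be detected.

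**What to change.** Keep the 7-day rule for deciding who is screened and treated in MSAT. Then:

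1. Add to 9.3: *For the M0-M12 prevalence comparison, participants with a falciparum-positive RDT who received any antimalarial treatment in the 3 weeks before the survey are excluded at both time points; a sensitivity analysis includes them at M0.*
2. Align 7.5 with the 3-week window in Appendix B, asked of all group 1 participants whatever their URDT result, and record the treatment date.
3. Reword 6.4.2 to match, so that it no longer depends on a complete course.

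The cost is one analysis sentence, one aligned history item and one edited criterion. The downside is one more question per group 1 participant at M0, which depends on recall of the treatment date. Screening and treatment in MSAT do not change.

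This aligns recent treatment only. M12 also excludes residents of under 4 weeks, and M0 excludes children under 1 year, with no counterpart in the other survey's list. Those differences remain unless the comparison is restricted for them too.

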6.3.3. Specific treatment regimen

Screening can be conducted on all village inhabitants but some specific population groups will require a specific treatment if they are found positive (see 8. Intervention)

6.4. Follow-up at 12 months (group 1 only)

6.4.1. Inclusion criteria

Randomly sampled individuals living in the village.

6.4.2. Exclusion criteria

- Individuals who do not provide informed consent.
- Individuals who have lived in the village for less than 4 weeks (newcomers residing elsewhere before)

- Individuals who had a falciparum positive RDT and received a complete ACT-treatment course during the 3 weeks before the survey.

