2. ABBREVIATIONS

ACT	Artemisinin Combination Therapy
AL	Artemether Lumefantrin
CE	Community engagement
DP	Dihydroartemisin-Piperaquin
ELISA	Enzyme Linked Immuno Sorbent Assay
GCP	Good Clinical Practice
GMS	Greater Mekong Subregion
HRP2	Histidin Rich Protein 2 (Plasmodial antigen detected by lateral flow assays: RDT or URDT)
ICF	Informed Consent Form
MDA	Mass drug administration
METF	Malaria Elimination Task Force
MP	Malaria Post
MSAT	Mass Screening and Treatment
NMCP	National Malaria Control Program
OxTREC	Oxford Tropical Research Ethics Committee
PI	Principal Investigator
PIS	Participant Information Sheet
PMQ	Primaquine
Q7C7	Quinine 7 days; Clindamycine 7 days
RDT	Rapid Diagnostic Test
sld PMQ	single low dose Primaquine
SOP	Standard Operating Procedure
uPCR	Ultrasensitive quantitative polymerase chain reaction
URDT	Ultrasensitive Rapid Diagnostic Test

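### M0 and M12 prevalence leave out recently treated people by different rules, and section 9.3 sets no common analysis population, so a small apparent fall is built in

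*Combined protocol and SAP*

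**What the plan says.** Section 4 makes the M0 survey, carried out during MSAT, the baseline for prevalence and compares it with the survey 12 months later. The two surveys have separate exclusion lists.

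- **M0 (6.3.2):** people with a documented positive RDT who received treatment "during the previous 7 days" are excluded. A note adds that people treated between 7 and 30 days before "are still likely to be URDT positive due to the persistence of HRP2", and that they are probably no longer infected.
- **M12 (6.4.2):** the exclusion is "Individuals who had a falciparum positive RDT and received a complete ACT-treatment course during the 3 weeks before the survey". It is longer, and it asks for a completed course rather than any treatment.

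For the analysis, section 9.3 says that "the fractional change in prevalence before MSAT and 12 months after will be calculated and compared to 0% change". It does not say that the two prevalences are computed on the same kind of population.

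The documents disagree on the history taken at Day 0. Section 7.5 says "History of malaria diagnosis and treatment during the previous week will be collected", among the steps that follow a positive URDT. Appendix B lists "Malaria history over previous 3 weeks" at Day 0, above the block for positive participants.

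**The concern.** A before/after change should reflect the intervention, not who was counted. Here one group, treated 8 to 21 days earlier, is in the M0 numerator and denominator and in neither at M12. If its members test positive more often than the rest of the village, as the note in 6.3.2 implies for the URDT, removing them only at M12 lowers the later figure. The shift points the same way in every village, so more villages do not average it out, and the prevalence comparison has no concurrent control that would reveal it.

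The reference assay is probably no safeguard. Section 7.7 names Quansys ELISA as the reference method, and Appendix D, Table 2 reports it as an HRP2 result. HRP2 is the antigen that section 2 describes as "Plasmodial antigen detected by lateral flow assays: RDT or URDT". That the ELISA shares the direction is an inference, since 6.3.2 speaks only of the URDT.

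**Working it through.** **The plan's own figure.** Section 9.2.2.2 uses 16% falling to 8%, 60 samples per cluster, ICC 0.15, alpha 0.05 and power 0.80. Two proportions, two-sided, pooled: (1.960·√0.2112 + 0.842·√0.208)² / 0.08² = 258 per period. Design effect: 1 + 59 × 0.15 = 9.85. Clusters: 258 × 9.85 / 60 = 42.4, so 43, as stated.

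**Inputs for the mismatch.**
- Prevalence P = 0.16 (9.2.2.2).
- Incidence I per 1000 per year: 84 (group 1 entry threshold, section 5), 125 (before MDA, 9.2.3), 250 (planning value, 9.2.1).
- Width of the mismatch: days 8 to 21, 14 days.
- Share s of these people still positive: the documents give no figure, so 0.5 to 1.0 is assumed.
- Incidence is spread evenly over the year (assumed).

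**Formulas.** Share of the village affected: f = (I/1000) × 14/365. M0 prevalence with these people removed: P′ = (P − s·f)/(1 − f). Apparent relative fall with no true change: 1 − P′/P.

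| I | f | P′ (s = 0.5) | Fall | P′ (s = 1) | Fall |
|---|---|---|---|---|---|
| 84 | 0.0032 | 0.1589 | 0.7% | 0.1573 | 1.7% |
| 125 | 0.0048 | 0.1584 | 1.0% | 0.1560 | 2.5% |
| 250 | 0.0096 | 0.1567 | 2.1% | 0.1519 | 5.1% |

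In a village of 190 (9.2.1), 190 × f is about 0.6 people at 84 and 1.8 at 250, against 190 × 0.16 = 30.4 positives.

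**Offset from the completed-course wording.** Read literally, someone in mid-course is dropped at M0 but counted at M12. With a 3-day course at 250/1000/year, that share is 0.250 × 3/365 = 0.00205. With all of them positive, the M12 figure becomes (0.16 − 0.00959 + 0.00205)/(1 − 0.00959 + 0.00205) = 0.1536, and the 5.1% case shrinks to about 4.0%. The direction is unchanged.

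**Effect on the planned contrasts (250/1000/year, s = 1, no offset).** An observed 50% fall is really 1 − 0.08/0.1519 = 47.3%. An observed 90% fall is really 1 − 0.016/0.1519 = 89.5%.

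**Effect on the test.** Under the model of 9.2.2.2 with 60 clusters of 60, the effective number per survey is 3600/9.85 = 365. At s = 1 the shift is 0.0027/0.0270 = 0.1 standard errors at 84/1000/year and 0.0081/0.0268 = 0.3 at 250. The two-sided error rate rises from 5.0% to between 5.1% and 6.1%.

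**Sensitivity.** The relative effect grows as prevalence falls. Over the 5-25% URDT positivity in section 3, which is not specific to group 1, it is 2.9-6.1% at 5% and 84/1000/year, and 1.0-2.9% at 25% and 250/1000/year. Recent incidence above the yearly average at the time of a survey would enlarge it; below, shrink it.

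**The case against.** **Size.** The strongest reply is that the effect is immaterial: one or two people per village, at most 0.3 standard errors in the planning model, and section 9.2.2.1 already accepts M12 intervals 100-200% as wide as the expected prevalence. That stands as a limit on importance. It does not remove a one-directional error that a sentence can prevent.

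**Different purposes.** M0 is an intervention round, and 6.3.2 gives a reason for screening people treated 7 to 30 days earlier. That justifies eligibility. It does not require them to be counted in the baseline prevalence. No section says that the MSAT exclusions define the prevalence analysis set, but none says otherwise. Text breaks off in 7.6.3 and 9.1, so the absence of a rule is judged on the text available.

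**The data are already scheduled.** Appendix B lists a 3-week history at Day 0, apparently for everyone. This stands, subject to the conflict with 7.5.

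Three stronger readings are tempting, and the documents do not support them:

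- *That the gap can never be closed later.* Section 5 says "No individual data will be collected to link clinical case participation, infection status and incidence of clinical episodes", but section 10.2 lists case-level falciparum data among what is recorded, and 12.4 keeps names in the MSAT logbook. The sections disagree, so retrieval from malaria post records should not be relied on, but it is not shown to be impossible.
- *That the MSAT versus MDA comparison is distorted.* The exclusion rules of the MDA surveys are not given. If they had the same mismatch, much of it would cancel.
- *That the residence and age rules add to the bias.* The minimum stay applies only at M12, and the M12 age limit is not stated, but no direction can be shown for either.

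**Conclusion.** The concern holds as a minor, avoidable bias in a secondary outcome. Followed as written, the plan counts people treated about 8 to 21 days earlier at M0 and drops them at M12, and the protocol's own note on HRP2 persistence gives the direction for the URDT. At 16% prevalence the spurious relative fall runs from about 0.7% to 5.1% over the incidences in the documents. These are upper-end figures for those inputs, because the completed-course wording works partly the other way.

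The result rests on two assumptions: 50-100% of the affected people still test positive, and incidence is even over the year. For the reference assay it also rests on the inference that the ELISA behaves like the URDT after treatment.

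A reader might infer that a reported fall of 50% or 90% could be an artefact. It could not: even the 5.1% case moves these only to 47.3% and 89.5%. The primary incidence outcome does not use these surveys and is unaffected.

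**What to change.** Leave MSAT screening and treatment eligibility unchanged. The change is to the analysis and to one item of data collection.

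1. In 9.3, state that M0 and M12 prevalence are computed on one common analysis population, with the same recent-treatment exclusion at both surveys: the same window, and the same choice between any treatment and a completed course. Applying the 3-week window to the M0 data would match the history in Appendix B.
2. Report the unrestricted M0 prevalence as a sensitivity analysis.
3. Reconcile 7.5 with Appendix B so that the treatment history covering that window is recorded at Day 0 for all group 1 participants, not only those who test positive.

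Aligning the minimum-stay and age rules between the surveys, and the two wordings of the stay (6.2 and 6.4.2), is optional tidying.

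The cost is a sentence or two in 9.3 and reconciled wording in 7.5 and Appendix B. The M0 set becomes slightly smaller and its prevalence slightly lower. With P′ at s = 1 as baseline, the requirement for a 50% fall moves from 43 clusters to 44 or 45, against 60 planned. With a 3-week rule, people treated 22 to 30 days earlier stay in both surveys, so some HRP2 persistence remains, but it is handled alike at both times. The change is easiest before M0 data collection, while the Day 0 history can still be secured.
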